Research Project Title

Assessing gestational age in first trimester pregnancies: A comparison of a new handheld wireless transabdominal ultrasound to a portable transabdominal ultrasound.

Research Question

This research project is designed to determine the equivalence of a handheld wireless (Clarius C3) transabdominal ultrasound to the current portable ultrasound with transabdominal and transvaginal capabilities (Zonare ZS3) when used to date first trimester pregnancies.

Background

There have been several new recommendations in the SOGC encouraging the provision of first trimester pregnancy ultrasound.

In the June 2018 SOGC Clinical Practice Guideline No 360-Induced Abortion: Surgical Abortion and Second Trimester Medical Methods, the authors write, “Ultrasound should be performed prior to induced abortion to confirm gestational age and aid in operative planning (Strong recommendation. Level of evidence: Low)”. In the SOGC Clinical Practice Guidelines on Medical Abortion published in 2016, they recommend that “women with significant risk factors, signs, or symptoms of ectopic pregnancy should have a pretreatment ultrasound before medical abortion”, but they does not require it to be performed. In patients who receive medical abortion (Mifepristone 200 mg orally followed by misoprostol 800 mcg buccally 24 to 48 hours) under 9 weeks’ gestation, the product monograph states that “ultrasound shall be performed before medical abortion”. It is the current standard at the sites that perform medical abortion in Manitoba (Women’s Hospital, Winnipeg Health Clinic Portage and Brandon Hospital) that an ultrasound is performed prior to medical abortion to confirm an intrauterine pregnancy. In March 2019, the SOGC developed a Clinical Practice Guideline on the Use of First Trimester Ultrasound. They recommended the following: “First trimester ultrasound is recommended to date a pregnancy (ideally at 7 to 12 weeks).”

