The cost of wireless portable ultrasounds that connect with a tablet computer or smart phone has made it more accessible for the average obstetrician/gynecologist going into practice. Canadian residents training in Obstetrics and Gynecology are now required to complete a month of training in ultrasound in their PGY1 year. If an inexpensive handheld ultrasound machine can be used to appropriately date a first trimester pregnancy, it would allow for the average obstetrician/gynecologist to appropriately date a pregnancy, regardless of their location. This would be highly valued in locations where ultrasound access by radiologists is not easily accessible.

In the SOGC practice guidelines Determination of Gestational Age (GA) by Ultrasound published February 2014, a mean sac diameter (MSD) is first used to date pregnancy using a transvaginal ultrasound when it is 2-3 mm or 32 to 33 days. The growth of the MSD is approximately 1 mm per day. Mean sac diameter becomes less reliable when it exceeds 14 mm or an embryo can be identified. A yolk sac or embryo seen inside the gestational sac in an intrauterine location provides confirmation that the pregnancy is definitely in the uterus. This makes an ectopic pregnancy extremely unlikely. The yolk sac usually becomes visible between 5 to 6 weeks GA. The embryo is usually seen after 6 weeks' GA. Crown rump length provides the most accurate estimate of gestational age when the embryo is clearly seen and it is reported to be accurate within 3-8 days. The SOGC recommend that crown rump length be used up to 84 mm in size (approximately 12 weeks and 4 days with Hadlock criteria), and the biparietal diameter be used for measurements greater than 84 mm. These criteria will be used to determine gestational age for the study.

Objective:

The objective of this study is to assess equivalency of the transabdominal Clarius handheld wifi C3 ultrasound (which uses Bluetooth to locate the iPad Mini 5 and then uses wifi direct to show the images) to the current standard of care in Women's Hospital outpatient department the portable Zonare ZS3 in patients presenting in the first trimester of pregnancy.

Research Design and Methodology

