completed medical abortion, completed surgical abortion (possibly following failed medical abortion), lost to follow up, continuing pregnancy, or ectopic pregnancy.

If a participant is determined to be over 13 weeks GA, they will receive a dating ultrasound with the Clarius C3 ultrasound using biparietal diameter as appropriate but it will not be included in the final study measurements.

For each participant, ultrasound reports and data from the "Research Participant Data Collection Form" will have a unique code and all information stored on a password-protected SPSS document on a locked desktop computer in the Research Office WS021 which is locked.

Sample Size

Sample size was estimated based on a one sided McNemar's test, 15% clinically significant difference (estimating 60% of subjects would allow a transabdominal ultrasound to see a gestational sac and a yolk sac with the Zonare ZS3 and 45% with the Clarius C3) at a power of .8 and alpha value of 0.05. This would require 131 participants to be recruited for the study.

Statistical Analysis

McNemar's test would be used to determine the ability of the transabdominal ultrasounds to measure the presence or absence of an intrauterine pregnancy. A paired t-test would be used to compare gestational sac measurements or crown rump lengths between the two ultrasound machines.

Inclusion Criteria

1. Presenting requesting medical or surgical abortion
2. Estimated to be under 13 weeks gestational age based on last menstrual period or time of conception, or nurses best estimate.
3. Able to provide informed consent with adult supervision of a minor or with an interpreter present

Exclusion Criteria

1. Unable to provide informed consent

Timeline

We anticipate data collection to occur over a 9-month period.

Budget

Data collection by the participating physicians will be on a volunteer basis. A medical student volunteer will not be paid for the procedure. Physicians who perform ultrasound for medical and surgical abortion will be reimbursed by Manitoba Health for their procedure with no additional funding for participation in the study. The study nurses involved in recruiting, consenting and collecting data will be paid by the Department of Obstetrics and Gynecology.

Conflict of interest

There is no conflict of interest identified in this study.

Discussion of Ethics*Informed consent*

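### Equivalent dating is the question, but the only measurement analysis is a paired t-test, with no margin, equivalence rule or agreement measure to support such a claim

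*Combined protocol and SAP*

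**What the plan says.** The Research Question asks about equivalence of the two machines "when used to date first trimester pregnancies", and the project title is also about assessing gestational age. The Objective section repeats the aim without naming dating: "The objective of this study is to assess equivalency of the transabdominal Clarius handheld wifi C3 ultrasound".

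The Statistical Analysis section has two sentences. One applies McNemar's test to whether an intrauterine pregnancy is seen on transabdominal scanning. The other reads "A paired t-test would be used to compare gestational sac measurements or crown rump lengths between the two ultrasound machines".

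The Background section sets out how sac diameter, crown rump length and biparietal diameter are used for dating, and adds "These criteria will be used to determine gestational age for the study". It also gives three figures on the scale of the measurements:

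- for sac diameter, "The growth of the MSD is approximately 1 mm per day";
- for crown rump length, "it is reported to be accurate within 3-8 days";
- for the upper end of the crown rump range, "approximately 12 weeks and 4 days with Hadlock criteria".

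The Sample Size section gives 131 participants, from a one-sided McNemar's test of 60% against 45% visibility of a sac and yolk sac. No primary endpoint is named.

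**The concern.** A paired t-test is built to find a non-zero mean difference; an equivalence question asks whether the difference is small enough. These need different analyses. Showing equivalence needs a statement, made beforehand, of how large a difference would still be acceptable, and a rule that compares the confidence interval with it. The plan has neither.

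A mean difference also says nothing about individual patients. Two machines can agree on average and still differ by several days in many women, in both directions. Dating is done one patient at a time, so that spread is what a user of the handheld device needs to know, and no planned analysis reports it.

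A secondary gap is that gestational age is to be determined for the study but enters no planned comparison. For sac pairs this matters little, because a millimetre is roughly a day. Days would, however, put sac and crown rump measurements on one scale, and would allow use of a pair in which one machine yields a sac and the other a crown rump length.

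At stake is the study's main conclusion: a margin chosen after the data are seen would carry little weight.

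**Working it through.** **1. What the plan's own figure covers.** The inputs are 60% and 45% visibility, one-sided alpha 0.05 and power 0.80 (Sample Size). The discordant proportion is not stated. Assuming independence between machines, it is 0.60 × 0.55 + 0.40 × 0.45 = 0.51. With unpooled variance, n = (1.645 + 0.842)² × (0.51 − 0.15²) / 0.15² = 134, within 3% of the stated 131. Other paired formulas give 137 to 139. So 131 is broadly reproducible, and it concerns detection only. Nothing in it sizes the measurement comparison.

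**2. Is there a margin elsewhere?** There are two candidates.

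- The 15-point difference is a detection difference that McNemar's test is powered to find. It is not in days or millimetres.
- The 3 to 8 days is background on the accuracy of crown rump dating. It is never adopted as a criterion for comparing machines.

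Neither supplies a margin for dating.

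**3. How many pairs?** The documents do not say. Three values span a range:

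- 131, every participant, a ceiling;
- 131 × 0.45 = 59, if everyone visible on the Clarius is visible on the Zonare;
- 131 × 0.60 × 0.45 = 35, under independence.

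The last two use sac-and-yolk-sac visibility as a proxy for measurability. A sac can be measured without a yolk sac, so more pairs are plausible.

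**4. What the t-test shows against what agreement looks like.** SDs of the paired difference, in days, are assumptions; the test is two-sided at 5%. At zero bias the limits of agreement are ±1.96 × SD, and the share beyond 3 days is 2 × [1 − Φ(3/SD)]. Three days is an illustrative cut, not a proposed criterion. The last column uses the non-central t distribution.

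| SD | Non-significant, zero bias | Limits of agreement | Differ by more than 3 days | True 1-day bias missed at 35 / 59 / 131 pairs |
|---|---|---|---|---|
| 1 | 95% | ±2.0 | 0.3% | under 1% / under 1% / under 1% |
| 2 | 95% | ±3.9 | 13% | 18% / 3.5% / under 1% |
| 3 | 95% | ±5.9 | 32% | 52% / 29% / 3% |
| 4 | 95% | ±7.8 | 45% | 70% / 53% / 19% |

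The first result column is constant while the next two change several-fold: at zero bias the test result carries no information about individual agreement.

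**5. What the proposed rules could deliver.** Rule (b) in the fix requires the 90% confidence interval for bias to lie within a mean margin. At SD 3, zero bias and a 1-day margin (all assumed), its power is 0.23 at 35 pairs, 0.62 at 59 and 0.97 at 131; 80% power needs 79 pairs. At a 2-day margin, 21 pairs suffice.

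Rule (a) uses the confidence bounds of the limits of agreement, with half-width 1.96 × SD × √[1/n + 1.96²/(2(n − 1))]. At SD 3 and 59 pairs this is 1.96 × 3 × √(0.01695 + 0.03312) = 1.32 days, so with observed bias 0 and SD 3 the outer bounds are about ±(5.88 + 1.32) = ±7.2 days. Requiring (a) as well as (b) lowers the power.

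**The case against.** The strongest reply is that a paired t-test normally comes with a mean difference and confidence interval, so the plan is not empty. This stands in part. A reader might infer that the plan gives no basis for any conclusion about dating, in either direction. The documents do not support that: a large mean difference with a tight interval would be evidence against equivalence even without a stated margin. What is missing is the means to support a positive claim.

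A reader might also infer that the investigators mean to read non-significance as equivalence. The plan never says so; this is an omission, not a stated false inference.

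On days, the reply is that millimetres of sac diameter are already close to days, and that one conversion applied to both machines maps equal sizes to equal ages. That is right, and it makes the lack of a comparison in days secondary to the missing margin and agreement measure.

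It can also be said that detection is the real endpoint, since only detection was sized. But no primary endpoint is named, and dating is in both the title and the research question.

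Finally, the illustration rests on assumed SDs. The Research Design and Methodology section has both scans usually done by the same provider, so an SD near 1 day is possible, and there the t-test would rarely miss a 1-day bias and few patients would differ by more than 3 days. This is fair. The point rests on logic; the table shows only what the test leaves unseen.

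**Conclusion.** The concern holds in a limited form and should be fixed before data are analysed. Followed as written, the plan yields a test of mean size difference and cannot support a positive claim that the handheld machine dates pregnancies equivalently. It could still yield evidence against equivalence.

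The absence of a margin, rule and agreement measure is a matter of text and needs no assumption. The size does: at zero bias the same 95% non-significance goes with limits of agreement anywhere from ±2.0 days (SD 1) to ±7.8 days (SD 4), and the documents give no SD to choose between them. The conclusion does not depend on 131 being wrong, and nothing here shows that 131 is too few.

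**What to change.** Make the paired difference in gestational age in days the measurement analysis, using the Background criteria and one named conversion applied identically to both machines. The plan mentions Hadlock criteria but gives no formula.

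- (a) Report Bland-Altman bias and 95% limits of agreement with confidence intervals. Require the outer confidence bounds of the limits to lie within an individual limit in days, fixed in advance.
- (b) Require the 90% confidence interval for bias to lie within a separate mean margin in days, fixed and justified before data are seen. The 3 to 8 day figure does not by itself justify either value.
- Claim equivalent dating only if (a) and (b) both hold. If only (b) holds, claim equivalence of mean dating only.
- (c) Use transabdominal-to-transabdominal pairs as the main comparison where the Zonare transabdominal measurement is recorded. Report pairs with a transvaginal Zonare measurement separately, so that machine and route are not mixed.
- (d) Include mixed sac and crown rump pairs in the main analysis, with a sensitivity analysis excluding them. Report how many participants lack a measurement on either machine.
- (e) Keep the paired t-test only as a descriptive secondary result. State as a limitation that the same provider usually scans with the Clarius first and that no blinding is described, which could narrow the differences.

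**Cost.** Two values in days and a conversion must be chosen and justified. The data collection form, which is not in the documents, must record each machine's measurement, its type and the route. The study may end without showing equivalence, especially with a tight margin and few measurable pairs. No extra participants are requested.

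### If the Clarius shows a sac and yolk sac but only the Zonare yields a crown rump length, neither planned analysis registers the miss

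*Combined protocol and SAP*

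**What the plan says.** The Research Question and Objective ask about equivalence "when used to date first trimester pregnancies". The Background sets the dating criteria and adopts them for the study:

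- Mean sac diameter (MSD) comes first: "Mean sac diameter becomes less reliable when it exceeds 14 mm or an embryo can be identified".
- CRL is the most accurate measure when the embryo is clearly seen, and "The embryo is usually seen after 6 weeks' GA".
- Biparietal diameter (BPD) takes over above a CRL of 84 mm, about 12 weeks 4 days.

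The Statistical Analysis section has two analyses. The first is binary: "McNemar's test would be used to determine the ability of the transabdominal ultrasounds to measure the presence or absence of an intrauterine pregnancy". The second is continuous: "A paired t-test would be used to compare gestational sac measurements or crown rump lengths between the two ultrasound machines".

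The Background lets either a yolk sac or an embryo confirm an intrauterine location. The Research Design and Methodology section agrees: a pregnancy counts as undocumented only if there is no sac, or a sac with neither a definite CRL nor a yolk sac. The sample size endpoint does not require an embryo either. It is the proportion in whom it is possible to "see a gestational sac and a yolk sac with the Zonare ZS3 and 45% with the Clarius C3", with 60% assumed for the Zonare.

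The only exclusion from the comparison for non-visualisation is pregnancy of unknown location. Nothing is said about a CRL obtained on one machine only, about MSD on one machine against CRL on the other, or about comparing derived gestational ages.

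**The concern.** Under the study's own criteria, dating depends on measuring the embryo once it is clearly seen. A handheld device could show the sac and yolk sac yet fail to resolve an embryo that the portable machine measures. That is an intermediate failure: enough to document an intrauterine pregnancy, not enough to give the preferred dating measurement.

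Neither analysis is built to see it. The study could report similar detection of intrauterine pregnancy and similar measurements, while the Clarius failed to give CRLs that the Zonare obtained. Any dating conclusion would then rest on pregnancies in which both machines gave the same type of measurement. The protocol expects the data to inform ultrasound in remote locations, where there may be no second machine to fall back on.

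**Working it through.** **1. The plan's own figure.** Inputs from Sample Size: "Sample size was estimated based on a one sided McNemar's test, 15% clinically significant difference", 60% against 45%, "at a power of .8 and alpha value of 0.05", N = 131. The discordant proportion is not given. Assuming the two machines are independent:

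- Zonare only: 0.60 × 0.55 = 0.33. Clarius only: 0.40 × 0.45 = 0.18. Discordant: 0.51.
- N = (1.645 + 0.842)² × (0.51 − 0.15²) / 0.15² = 134.

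This is within 3% of 131. Other one-sided formulas under independence give 136 to 145. The point below does not depend on the 131.

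**2. When the criteria call for CRL.** From the Background, MSD is 2–3 mm at 32–33 days and grows about 1 mm per day. It therefore reaches 14 mm between 32 + (14 − 3) = 43 days and 33 + (14 − 2) = 45 days, that is 6w1d to 6w3d. This fits the statement that the embryo is usually seen after 6 weeks. Enrolment runs to an estimated 13 weeks.

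**3. How the pair is scored.** The Clarius shows sac and yolk sac with no measurable embryo; the transabdominal Zonare gives a CRL.

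- McNemar's test: positive on both machines, so the pair is concordant and does not enter the statistic.
- t-test on CRL: no Clarius value, so no pair.
- t-test on sac size: a pair exists only if the operator also recorded an MSD on the Zonare. It compares a measure that the Background calls less reliable at that stage, and it does not show that a CRL was missed.
- On the literal sample size endpoint (sac plus yolk sac), the pair is again concordant. If no yolk sac was recorded on the Zonare, it would count against the Zonare instead.

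**4. Effect on the planned statistics.** z = (b − c)/√(b + c), where b is Zonare only and c is Clarius only. The share positive on both machines is assumed, because the plan does not give it. The missed share is the assumed percentage of both-positive pairs with a CRL on the Zonare only. CRL pairs are upper limits, taking every both-positive pair as a possible CRL pair.

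| Both positive | b | c | z at 0, 10, 20 and 40% missed | Most CRL pairs at 0 / 10 / 20 / 40% |
|---|---|---|---|---|
| 27% (35 pairs, independence) | 43 | 24 | 2.32 throughout | 35 / 31 / 28 / 21 |
| 35% (46 pairs) | 33 | 13 | 2.95 throughout | 46 / 41 / 37 / 28 |
| 44% (58 pairs) | 21 | 1 | 4.26 throughout | 58 / 52 / 46 / 35 |

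A simulation of the t-test on complete pairs started from 131 pairs, with no measurement bias and with misses unrelated to the size of the difference. Rejection stayed at 4.3% to 5.6% for 0 to 40% missed. The t-test loses pairs but gives no signal of the failure.

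**5. What a direct comparison would see.** Suppose both machines agree on intrauterine pregnancy in all 131, and in k participants only the Zonare gives a CRL (k is assumed). The planned McNemar's test has no discordant pairs, so p = 1 whatever k is. A McNemar's test on CRL obtained has k against 0, with one-sided exact p = 0.5^k: 0.031 for k = 5 and 0.001 for k = 10.

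**The case against.** **MSD remains a measurement.** The Background says less reliable above 14 mm or once an embryo is seen, not unusable. A reader might infer that these pregnancies cannot be dated on the Clarius; the documents do not say so. A sac pair may also exist for the t-test. Both points stand. What remains is that the Clarius did not give the preferred measurement and no analysis records it.

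**McNemar's test already catches worse failures.** If the Zonare documents an intrauterine pregnancy and the Clarius shows neither yolk sac nor embryo, the pair is discordant and counts against the Clarius. On the planning rates the Zonare-only pairs number between 0.15 × 131 = 20 (Clarius positives nested within Zonare positives) and 0.33 × 131 = 43 (independence), and all of them are counted. It would be wrong to infer that every failure to resolve the embryo escapes. Only the intermediate kind does.

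**Calendar days are not participants.** A reader might note that about 46 of the 59 days from day 32 to day 91 fall after day 45, and infer that most participants need a CRL. The documents give no distribution of gestational age, medical-abortion participants are prescreened to under 9 weeks, and the last few days use BPD. No share of participants follows.

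**The comparison must be fair to the Clarius.** The Zonare also has transvaginal capability, whereas McNemar's test is worded for transabdominal scans. An embryo seen only transvaginally should not count as a Clarius failure. This stands and shapes the fix.

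**Dropping out is inferred.** The plan has no rule for a measurement missing on one machine, so the loss of the pair follows from how a paired t-test works, not from a stated exclusion.

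**Conclusion.** The concern holds for one intermediate failure: the Clarius shows a sac and yolk sac, the transabdominal Zonare gives a CRL, and neither planned analysis detects the difference. This follows from the plan's definition of a documented intrauterine pregnancy and from the nature of a paired t-test, and it does not depend on N.

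The frequency of this failure cannot be derived from the documents. The missed shares, both-positive shares and values of k above are assumptions that show how the tests behave; they are not forecasts. The documents do not support saying that these pregnancies are undatable on the Clarius, or that they form a large share of participants.

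The gap is more than missing detail. The plan could be followed exactly and still leave part of the dating question unanswered, so it should be closed before analysis.

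**What to change.** Keep McNemar's test on intrauterine pregnancy, and add the following.

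1. **A paired yes/no outcome per machine**, on transabdominal images only and on all scanned pairs included in the comparison: was a measurement usable under the Background criteria obtained? Yes means a CRL, or a BPD in its range, or an MSD of at most 14 mm where neither transabdominal scan identified an embryo. Compare it with McNemar's test. A CRL obtained on one machine only counts as a failure of the other, in either direction.
2. **A cross-table** of the most advanced structure seen (none, sac, yolk sac, CRL), Clarius by transabdominal Zonare.
3. **Like-for-like t-tests**: sac with sac, CRL with CRL. Limit the sac comparison used for dating to pairs meeting the 14 mm and no-embryo rule. State how many pairs are left out and why.

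The new outcome scores a larger sac, or a sac with an embryo seen on either machine, as not meeting the criteria. This is a definition for the analysis and should be reported as such; the cross-table lets readers apply another.

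**Cost.** Protocol wording and one derived variable, with no extra scan. The Clarius success rate may look lower than on a yolk-sac endpoint. The 60% and 45% planning rates do not apply to the added outcome, so its expected rates and power need stating. The data collection form is not shown; the sponsor should confirm that it records each structure by machine and by scan route.
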